14.3 Analysis of Primary Endpoint

We will examine the distribution of 25(OH)D₃ clearance by CF status using box plots and summary statistics. We will explore the distribution of 25(OH)D₃ clearance by key covariates (age, gender, and baseline concentrations of 25(OH)D, PTH, FGF-23, and vitamin D binding protein) using locally weighted scatterplot smoothing (LOWESS), cubic splines, and box plots. We will pay particular attention to the associations of PTH and FGF-23 with 25(OH)D₃ clearance, including multivariable modeling to determine independent associations. We will test associations of CF status with 25(OH)D₃ clearance (continuous outcome variable) using linear regression. Models will be adjusted for age, gender, body size, baseline 25(OH)D concentration, and other covariates strongly related to 25(OH)D₃ clearance.

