5 CRITERIA FOR EVALUATION

5.1 Primary Efficacy Endpoint

The primary outcome of interest is the metabolic clearance of labeled 25(OH)D₃.

We will measure serum concentrations of 24,25(OH)₂D₃, 25(OH)D₃, 25(OH)D₂, 1,25(OH)₂D₃ and 1,25(OH)₂D₂ at the University of Washington by mass spectrometry. For each participant and time point, a single serum aliquot is used to measure this panel of vitamin D metabolites using by immunoaffinity extraction and HPLC-mass spectrometry (Xevo TQ, Waters Corp., Milford, MA) with deuterated internal standards.^{25,30-32}

For each subject, non-compartmental analysis of plasma concentration versus time data will be performed using Phoenix software (Pharsight, Cary, NC). Clearance will be calculated as administered 25(OH)D₃ dose divided by 25(OH)D₃ AUC. We focus on clearance as our primary outcome because it reflects the metabolism of 25(OH)D₃ accounting for circulating 25(OH)D₃ concentration (units of volume/time, akin to creatinine clearance). Clearance is independent of volume of distribution, in contrast to $t_{1/2}$, which will be evaluated as a secondary outcome. Clearance will be evaluated with and without adjustment for body size.

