5.2 Secondary Efficacy Endpoints

- AUC of labeled 25(OH)D₃
- Terminal half-life of labeled 25(OH)D₃
- Volume of distribution in the central compartment of labeled 25(OH)D₃
- Metabolic formation clearance (metabolite/parent AUC ratio) for metabolites of labeled 25(OH)D₃
- Monocyte transcription of CYP27B1, CYP24A1, VDR, and cathelicidin

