14.4 Analysis of Secondary Endpoints

Analyses of secondary endpoints will parallel those of the primary endpoint.

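### Sections 14.3 and 14.4 fix no analysis scale, and AUC is to be tested without normalising for a dose that differs between participants

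*Combined protocol and SAP*

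**What the plan says.** Section 14.3 examines clearance by CF status "using box plots and summary statistics", explores covariates with smoothers, then fits clearance as a "continuous outcome variable) using linear regression". It adds: "Models will be adjusted for age, gender, body size, baseline 25(OH)D concentration, and other covariates". No transformation, geometric mean or rule for choosing a scale appears, and no action is tied to the box plots.

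Section 14.4 is one sentence: "Analyses of secondary endpoints will parallel those of the primary endpoint". Section 5.2 lists what that covers: "AUC of labeled 25(OH)D₃", terminal half-life, central volume, metabolite/parent AUC ratios and "Monocyte transcription of CYP27B1, CYP24A1, VDR, and cathelicidin".

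Section 5.1 defines the primary endpoint: "Clearance will be calculated as administered 25(OH)D₃ dose divided by 25(OH)D₃ AUC". Section 8.4.1 sets dose individually as 5 ng/mL times estimated blood volume. It allows the approach to be revised for later participants, with a doubling given as an example. Section 14.6 bases the sample size of 20 on feasibility and funding.

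**The concern.** There are two gaps, and they meet in AUC.

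First, the scale is open. These endpoints are positive quantities, several of them ratios, for which a log scale is a standard choice. If they are right-skewed, a raw-scale regression with 20 people gives away power. If the scale is chosen after the box plots are seen, the choice is post hoc.

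Second, clearance is already divided into dose, but AUC is not. Two participants with the same clearance and different doses have different AUCs. A group difference in blood volume, or a dose revision that falls unevenly, would appear in the AUC comparison as if it were a metabolic difference; a revision that falls evenly adds noise. Section 6.1 matches on age, gender and race, not body size.

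At stake is the reading of the secondary endpoints, and whether AUC appears to contradict the primary result.

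**Working it through.** **Inputs from the documents.** 10 CF and 10 controls (section 4); four named covariates (14.3), so intercept + CF + 4 = 6 parameters and 20 − 6 = 14 residual degrees of freedom; clearance CL = dose/AUC (5.1); dose = 5 ng/mL × blood volume (8.4.1).

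**Assumed, because the documents are silent.** Two-sided 0.05; log-normal clearance with CV 20–100%; CF/control ratios 1.0–2.0; dose CV 0–20%. Figures are simulated, 20,000–40,000 trials per setting, with clearance independent of dose.

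**The plan's own figures.** There is no power statement to reproduce. The typical dose does reproduce: 5 mcg/L × 5–6 L = 25–30 mcg. That range also gives the size of the dose effect. Since AUC = dose/CL, two people with equal clearance at its ends differ in AUC by 30/25 = 1.20, or 20%. Doubling the dose doubles AUC.

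**Which endpoints dose affects.** Clearance is already dose-normalised. Under linear kinetics, dose also cancels from half-life, volume and metabolite/parent ratios. Only AUC carries it.

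**Lower CF dose, equal clearance (CL CV 30%, dose CV 15%).** By hand for log AUC, no covariates: shift = |ln 0.85| = 0.1625; SD = √(ln 1.09 + ln 1.0225) = √(0.0862 + 0.0223) = 0.329; standardised shift 0.494; noncentrality 0.494 × √5 = 1.10; rejection rate on 18 df = 18%. With four covariates unrelated to dose, the raw AUC test rejects in 14%, and in 9% if CF doses are 10% lower. Clearance stays at 5%.

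The plan does adjust for body size, which helps. With CF doses 15% lower and a size covariate correlated with log dose within group:

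| Correlation | Raw AUC rejects |
|---|---|
| 0.5 | 10% |
| 0.7 | 7% |
| 0.8 | 6% |
| 0.9 | 5% |

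**Dose doubled for 14 of 20 in random order (true ratio 1.5, CL CV 30%, dose CV 15%).** Power is 69% for raw clearance or raw dose-normalised AUC. For un-normalised AUC it is 59% without the doubling and 36% with it. A size covariate correlated 0.8 or more with unrevised log dose lifts the last figure only to 38–40%, because body size carries no information on the revision.

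**Raw versus log scale (log-normal clearance, four null covariates).** Disagreement means that one of raw CL and raw dose-normalised AUC has p<0.05 and the other does not.

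| CV | Ratio | Power raw | Power log | Disagreement |
|---|---|---|---|---|
| 30% | 1.25 | 28.1% | 29.3% | 8.8% |
| 30% | 1.5 | 68.9% | 71.5% | 10.7% |
| 30% | 2.0 | 97.7% | 98.7% | 2.2% |
| 40% | 1.5 | 45.6% | 49.4% | 14.5% |
| 60% | 2.0 | 54% | 63% | 21% |
| 100% | 2.0 | 24.4% | 34.2% | 21.3% |

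Type I error with these covariates is 4.3–4.9% raw and 5.0% log. On the log scale, log(AUC/dose) = −log CL, so those two tests are identical and disagreement is 0%.

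**Logging without normalising.** At CL CV 30% and ratio 1.25, without covariates, log CL and log AUC still disagree in 10.8% of trials at dose CV 10% and in 18.9% at dose CV 20%. With log dose in the model, disagreement is 0%.

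**If clearance is normal instead (no covariates).** Logging costs power: 75.0% to 74.1% (SD 20% of the control mean, +25%); 42.4% to 39.9% (SD 30%, +25%); 42.4% to 36.5% (SD 30%, −25%).

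**The case against.** The strongest case against is that little turns on this. The study is labelled descriptive, its size was set by feasibility, and no alpha or success rule is stated, so discordant p-values trigger no decision. The raw-scale test keeps its type I error. The larger power gains need CVs of 60–100%, which nothing in the documents supports for clearance. Section 14.3 is silent on scale rather than wrong, since log clearance is also a continuous outcome. All of this stands, and it keeps the point minor.

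The body-size adjustment is a fair answer to the 14% figure. Dose is computed from estimated body size, so a well-chosen size covariate removes most of that excess. A 15% gap in mean dose is also nearly the whole typical range (25/30 = 0.83). What survives is that the size measure is not named and cannot capture a dose revision.

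A reader might infer four stronger claims that the documents do not support:

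- That the plan prescribes untransformed outcomes. This is inferred; the text never says it.
- That AUC is clearance inverted. It would be at constant dose, but dose is individual and revisable.
- That logging alone reconciles the two. It does so only with dose normalisation, or with log dose in the model.
- That logging is free. It changes the estimand to a ratio, loses a little power if data are near normal, and fails on zero or below-detection values without a rule. The documents do not give the unit of expression; if it is already a log-type measure, logging again would be wrong.

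**Conclusion.** The point holds as a gap in pre-specification with an inexpensive remedy. The analysis scale is unstated for every endpoint under 14.3 and 14.4, and AUC is not separated from dose.

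The dose issue matters more. AUC can show a group difference when clearance is equal: about 14% rejection with CF doses 15% lower and no covariate tracking dose, falling to 5–6% if body size tracks dose closely. AUC can also miss a real difference after a dose revision, with power of 36–40% against 69%.

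The scale issue is small for clearance at CV 30% (1–3 points). It reaches 9–10 points only at CV 60–100%, and only if the data are log-normal. Every size given here rests on assumed CVs, ratios and dose differences. The primary clearance test is valid as planned, and nothing here suggests a false primary conclusion.

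**What to change.** In 14.3 and 14.4:

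- State that clearance, half-life, volume and AUC ratios are analysed after log transformation. Do the same for expression unless it is already on a log-type scale, and state its unit.
- Report CF/control geometric mean ratios with 95% CIs; keep raw means and box plots as descriptive.
- In 5.2, replace AUC by dose-normalised AUC, or keep AUC descriptive only. Say that log dose-normalised AUC repeats the log clearance test with the sign reversed, so it is not counted as separate evidence.
- Give a rule for zero and below-detection metabolite or transcript values.

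The cost is a few SAP sentences and no new data, visits or participants. The downsides are that effects become ratios instead of differences, and that a small amount of power is lost if the data turn out nearer to normal.

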4 STUDY DESIGN

This is a cross-sectional, observational study that uses the intravenous administration of stable isotope-labeled 25(OH)D₃ to evaluate the metabolic clearance of 25(OH)D₃. It is a single-dose, open-label PK study of 25(OH)D₃.

We will recruit a total of up to 20 study subjects: 10 with and 10 without CF. Subjects who provide written informed consent and qualify at screening will receive a single dose of intravenous labeled 25(OH)D₃. Subsequent blood draws and urine collections will be used to determine the metabolic clearance of 25(OH)D₃ and related parameters.

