6 SUBJECT SELECTION

6.1 Study Population

We will target enrollment of 10 patients with CF and 10 healthy controls matched on age, gender, and race. To recruit the 10 CF patients, we will first turn to observational studies of CF for which participants have already granted consent for contact for additional research studies. If sufficient participants are not identified through this route, we will recruit directly from the University of Washington CF clinic. The 10 matched healthy controls will be drawn from the Healthy Kidney Study. Clinical data and contact information for these control subjects are contained in the Kidney Research Institute biorepository.

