9.1.2 Demographics

Demographic information (date of birth, gender, race) will be recorded at Screening.

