14.2 Demographic and Baseline Characteristics

The following demographic variables at screening will be summarized by CKD status and race: age, gender, medical comorbidities, medications used, height, weight, body mass index, laboratory values (including calcium, phosphorus, albumin, vitamin D binding protein, parathyroid hormone, fibroblast growth factor-23), and adiposity measured by DXA.

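### Race is a matching factor but not a prespecified covariate in the primary CF regression, so the CF interval may be somewhat conservative if race predicts clearance (minor, cheap to fix)

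*Combined protocol and SAP*

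**What the plan says.** Section 6.1 sets the design: "We will target enrollment of 10 patients with CF and 10 healthy controls matched on age, gender, and race". Section 4 gives the size: "We will recruit a total of up to 20 study subjects: 10 with and 10 without CF". Neither section says whether matching is individual or by frequency.

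Section 14.3 names the only test of the CF contrast: "We will test associations of CF status with 25(OH)D₃ clearance (continuous outcome variable) using linear regression". The adjustment follows: "Models will be adjusted for age, gender, body size, baseline 25(OH)D concentration, and other covariates". Four terms are fixed, and the open clause that ends the list reads in full "other covariates strongly related to 25(OH)D₃ clearance". The primary analysis entry in the synopsis uses the same model. Neither place has a pair term, a race stratum or a matched-pair variance, and no rule says how strong a relation must be for a covariate to enter. Race is also missing from the key covariates that section 14.3 lists for exploration (age, gender, 25(OH)D, PTH, FGF-23 and vitamin D binding protein). Section 14.4 extends the same approach to the secondary endpoints.

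Race will be available: "Demographic information (date of birth, gender, race) will be recorded at Screening" (section 9.1.2). Section 14.2 also uses it to lay out the baseline table: "The following demographic variables at screening will be summarized by CKD status and race".

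**The concern.** Matching on a factor makes the two groups alike on it, so its contribution cancels from the CF-control difference. The model-based standard error reflects that gain only if the factor is also in the model. Otherwise the factor's variance remains in the residual, and the standard error describes a noisier comparison than the one made. Age and gender are handled properly; race is not, and no reason is given.

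What is at stake is precision on the primary contrast. The number of participants was set by what was feasible and funded (section 14.6), so the analysis is where precision can still be gained. There is also a prespecification issue: whether a design factor enters the model would depend on how it relates to the outcome data, under a clause with no threshold.

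**Working it through.** **No figure to reproduce.** The plan states no standard error, SD, effect size, alpha, power or interval width. The check therefore compares two models under stated assumptions.

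**Inputs from the documents**
- N = 20, 10 with and 10 without CF (section 4).
- Matching on age, gender and race (section 6.1).
- Model A, as named in section 14.3: intercept, CF, age, gender, body size, 25(OH)D. Residual df = 20 - 6 = 14.
- Model B: Model A plus a two-level race term. Residual df = 20 - 7 = 13.

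**Assumptions, not in the documents**
- Residual SD 1; race effect on clearance 0 to 1.5 SD; 1 to 3 of the 10 pairs in the minority race group.
- Exact matching on age, gender and race.
- Body size and 25(OH)D unrelated to race.

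**Step 1: analytic width ratio.** With race orthogonal to CF and R² the sample partial R² of race:

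width(B)/width(A) = (t13/t14) × √[(1 - R²) × 14/13]

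Here t14 = 2.1448 and t13 = 2.1604, so t13/t14 = 1.0073 and √(14/13) = 1.0377.

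| Sample partial R² of race | Width with race / without race |
|---|---|
| 0 | 1.045 |
| 0.05 | 1.019 |
| 0.085 | 1.000 |
| 0.10 | 0.992 |
| 0.20 | 0.935 |
| 0.30 | 0.875 |

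Break-even: R² = 1 - (13/14) × (2.1448/2.1604)² = 0.085. Below this, adding race widens the interval; above it, adding race narrows it.

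The first row overstates the expected cost of an irrelevant race term. With no true effect, the sample partial R² still averages about 1/14 = 0.071, which gives 1.0453 × √(1 - 0.071) = 1.007. The simulated cost is about 1.1%.

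**Step 2: simulation, 8,000 runs per setting.** Mean 95% interval width without race divided by width with race:

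| Race effect | 1 minority pair | 2 pairs | 3 pairs | Coverage without race |
|---|---|---|---|---|
| 0 SD | 0.989 | 0.989 | 0.989 | about 95% |
| 0.5 SD | 0.999 | 1.008 | 1.015 | 95.0-95.5% |
| 1 SD | 1.033 | 1.062 | 1.085 | 95.8-96.8% |
| 1.5 SD | 1.082 | 1.152 | 1.193 | 96.6-97.7% |

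Coverage with race stays near 95% throughout. Without race, the mean error of the CF estimate lies between -0.014 and +0.009 SD in these settings, which is simulation noise. If there are no minority pairs, the race term cannot be estimated and leaving it out changes nothing.

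**The case against.** **The condition.** The interval is too wide only if race predicts clearance well enough to repay a degree of freedom. At a 0.5 SD race effect the difference is at most 2%; with no effect, adding race makes the interval slightly wider. This stands, and it limits the point to a conditional one.

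**Larger figures need large race effects.** A reader might take race explaining 20% of otherwise unexplained variance as a modest case. In a separate simulation (2,500 runs per setting) it gives a half-width of 1.23 against 1.12 SD, and power for a 1.5 SD CF difference of 68% against 74%. Solving p(1 - p)d² / [p(1 - p)d² + 1] = 0.20 gives d of about 1.1, 1.25 and 1.7 SD for 3, 2 and 1 minority pairs of 10. At 30%, d is about 1.4, 1.6 and 2.2 SD. Nothing in the documents supports effects of that size, so these figures should not headline the point.

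**The open clause may admit race.** A covariate strong enough to matter is a natural candidate for that clause. It is therefore wrong to infer that the plan excludes race; it only fails to prespecify it. But the clause has no selection rule and race is not among the covariates listed for exploration, so its entry is left to the data.

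**The error is on the safe side.** With race balanced, the estimate is unbiased and coverage is at or above nominal, in a study the sponsor calls descriptive. This stands and lowers the severity. A reader might go further and infer bias, because the model conditions on baseline 25(OH)D: if race shifted both 25(OH)D and clearance, balance given 25(OH)D could be lost. The documents give neither relation, so that cannot be claimed.

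**A race term is not a paired analysis.** True. If matching is individual, the regression remains unpaired even with race in it. The term deals with race only.

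**Conclusion.** The point holds as a minor, conditional one. Race is the only matching factor not fixed in the primary CF model, and no matched analysis takes its place. If race predicts clearance and is balanced by matching, the model-based interval without it is conservative and the CF estimate is not biased.

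The size cannot be settled from the documents. Under the assumptions above, it runs from a 1% gain in width to a 19% loss; the loss passes 10% only at a 1.5 SD race effect with 2 or 3 minority pairs. The documents do not support two stronger readings: that the plan states an incorrect standard error (it states none), or that the interval is certain to be too wide. The case for change rests on cost: the downside of naming race is small and bounded, while the benefit could be material in a 10-against-10 comparison.

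**What to change.** In section 14.3 and the primary analysis entry of the synopsis, list race with age and gender as a fixed covariate in the primary CF model, whatever its observed relation to clearance. Code it in two levels if categories are sparse, and drop it only if all participants share one race. Section 14.4 then follows without further change. One added sentence in section 6.1 on whether matching is individual or by frequency would help the reader judge the unpaired regression.

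Cost: one residual degree of freedom (14 to 13) and about 1-2% in interval width if race is unrelated to clearance. No new data are needed, since race is already recorded at screening.

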DURATION OF SUBJECT PARTICIPATION AND DURATION OF STUDY	Subjects will be on study for approximately 12 weeks Screening: approximately 4 weeks Treatment: 1 day (subjects to the University of Washington Clinical Research Center) Follow-up: 8 weeks The total duration of the study is expected to be up to 3 years for subject recruitment and an additional 12 weeks for final subject follow-up.
CONCOMITANT MEDICATIONS	Allowed: 
Vitamin D supplements (cholecalciferol, ergocalciferol) not to exceed a mean daily dose of 400 IU Prohibited (within last 3 months, wash-out allowed): 
1,25(OH)₂D₃ or an analogue (e.g. paricalcitol, hectorol)Calcimimetics (e.g. cinacalcet)Medications known to potently induce or inhibit CYP24A1 or CYP3A4
EFFICACY EVALUATIONS	None
PRIMARY ENDPOINT	
Metabolic clearance of labeled 25(OH)D₃ (administered dose/AUC)
SECONDARY ENDPOINTS	
AUC of labeled 25(OH)D₃Terminal half-life of labeled 25(OH)D₃Volume of distribution in the central compartment of labeled 25(OH)D₃Monocyte transcription of CYP27B1, CYP24A1, VDR, and cathelicidin
OTHER EVALUATIONS	Metabolic formation clearance (metabolite/parent AUC ratio) for metabolites of labeled 25(OH)D ₃
SAFETY EVALUATIONS	Change in the serum concentrations of calcium, creatinine, AST, and ALT and from baseline to 7 days after 25(OH)D ₃ administration Incidence of adverse events

PLANNED INTERIM ANALYSES	This is not a clinical trial with an efficacy outcome, and it is neither randomized nor blinded. For interim analyses are not planned.
STATISTICS Primary Analysis Plan	We will examine the distribution of 25(OH)D ₃ clearance by CF status using box plots and summary statistics. We will test associations of CF status with 25(OH)D ₃ clearance (continuous outcome variable) using linear regression. Models will be adjusted for age, gender, body size, baseline 25(OH)D concentration, and other covariates strongly related to 25(OH)D ₃ clearance.
Rationale for Number of Subjects	For this descriptive study, our sample size of 20 was based on feasibility and funding considerations.

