14.6 Sample Size and Randomization

For this descriptive study, our sample size of 20 was based on feasibility and funding considerations.

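### The primary CF model admits covariates chosen after clearance has been explored, under an open rule; depending on how it is applied, an assumed 5% error rate becomes anything from about 1% to about 20%

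*Combined protocol and SAP*

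**What the plan says.** Section 14.3 (Analysis of Primary Endpoint) first explores clearance against age, gender and baseline 25(OH)D, "PTH, FGF-23, and vitamin D binding protein", using smoothers, splines and box plots. It gives particular attention to PTH and FGF-23, "including multivariable modeling to determine independent associations". It then turns to the primary comparison ("We will test associations of CF status with" clearance, by linear regression) and sets the adjustment: "Models will be adjusted for age, gender, body size, baseline 25(OH)D concentration, and other covariates strongly related to" clearance. The open part of that rule is its last clause, "other covariates strongly related to" clearance. The Statistics entry of the synopsis repeats the adjustment rule, and Section 14.4 has the secondary analyses follow the primary one.

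Section 4 gives the size: "We will recruit a total of up to 20 study subjects: 10 with and 10 without CF". Section 14.6 calls the study descriptive and says that "our sample size of 20 was based on feasibility and funding considerations". No significance level, candidate list, entry threshold, limit on added terms or selection procedure is stated.

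**The concern.** How strongly a covariate is related to clearance is a property of the outcome data, so the final adjustment set depends on those data. The standard regression p-value and interval for CF treat the set as if it had been fixed beforehand.

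The sample leaves little room for this. Intercept, CF and four one-degree-of-freedom adjusters use 6 of 20 degrees of freedom, leaving 20 − 6 = 14, and each added term takes another.

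The three named extra candidates are also not neutral. Section 2 says that PTH and FGF-23 regulate the vitamin D metabolic enzymes and that binding protein may be lost in urine in CF. If such a marker carries part of the CF effect, a model with it and a model without it answer different questions, and the data would decide which is reported.

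**Working it through.** **Plan's own figure.** There is none to reproduce: no alpha, power, effect size or SD is given, and N = 20 rests on feasibility and funding.

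**Inputs from the documents.** 10 CF and 10 controls (Section 4); age and gender matched (Section 6.1); four fixed adjusters; three further named candidates (Section 14.3).

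**Assumptions.** Two-sided 5%; normal errors; entry at p<0.05 or p<0.20; candidates shifted by 0 or 1 SD in CF; a wider pool of 8. Section 14.2 lists other measured variables, such as calcium, phosphorus, albumin and adiposity, which makes a wider pool possible, but the figure of 8 is mine.

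**Method.** Simulate trials with no CF effect, choose covariates, refit, and count how often the CF term has p<0.05:

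type I error = (trials with CF p<0.05 in the final model) / (trials simulated).

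The Monte Carlo SE is √[p(1−p)/n]. For example, √(0.0553 × 0.9447 / 1,500) = 0.0059, or 0.6 points. The forward-selection cells use 1,500 trials and the one-at-a-time cells 3,000.

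**Results with pure-noise candidates (% of trials).** The four figures in each cell are, in order: no shift p<0.05; no shift p<0.20; 1 SD shift p<0.05; 1 SD shift p<0.20.

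| Selection | CF ignored at selection | CF in selection model |
|---|---|---|
| One at a time, 3 candidates | 4.8, 5.7, 4.3, 3.5 (univariate) | 5.7, 7.6, 7.4, 10.0 |
| Forward, 3 candidates | 4.2, 4.7, 3.1, 2.5 | 5.5, 7.0, 6.7, 10.5 |
| Forward, 8 candidates | 6.1, 4.6, 1.6, 0.9 | 8.9, 13.3, 12.9, 21.1 |

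The mechanism fits the pattern. If CF is ignored, a chosen covariate that differs by CF absorbs variation the CF term would otherwise carry, so the test becomes conservative. If CF is in the model, covariates are kept for their chance relation to clearance given CF. That shifts the CF coefficient and makes the residual variance too small.

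**Other readings, three candidates.**
- Reporting whichever adjusted model has the smallest CF p-value: about 8–9% with no shift, 13% with a 1 SD shift.
- One candidate truly affects clearance (coefficient 0.5 or 0.8) and differs by 1 SD in CF, with CF in the selection model: 8.5–12.5% rejection of a zero direct CF effect.

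Together, the three-candidate results under these less favourable readings span roughly 6–13%. Further runs of the 8-candidate case with CF in the model gave 8–20% and 9–17%, so I quote about 8–20%; the 21.1% cell has an SE of 1.1 points.

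**Fixed sets.** With no CF effect, the four named adjusters alone give 3.8–6.3% across cells, which is simulation noise around 5%. The four plus all three candidates give 4.3–5.3%.

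**Change of target.** Where a candidate affects clearance and differs by 1 SD in CF, the CF effect transmitted through it is 0.5 × 1 = 0.5 or 0.8 × 1 = 0.8. The four-adjuster model then rejects in 13–24% of trials. Against a target that includes the pathway, that is power; against the direct effect, it is error. The plan has to say which it wants.

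**The case against.** A reader might infer that putting covariates related to the outcome into the model inflates the false-positive rate in itself. The documents do not support that. Section 14.3 selects on relation to clearance, not on the CF result, and its graphical exploration is closest to selection that ignores CF. On that reading the rate stays near or below 5%, and a shift of the candidates in CF makes the test more conservative. This part of the objection stands.

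A reader might also infer that stepwise building of the CF model is planned. No stepwise method is named. The multivariable modelling sentence concerns PTH and FGF-23 as correlates of clearance, which matches a separate secondary objective in Section 3.2. CF in the selection model is therefore a reading the text permits, not one it states. Likewise, Section 14.3 names only three extra candidates; the higher rates need a wider pool.

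Finally, the study is called descriptive, is meant to generate hypotheses, and sets no alpha, so 5% is my benchmark. That limits the weight of the point but does not remove it. Section 14.3 does say that it will test the association with CF, and a confidence interval that ignores selection can mislead in a descriptive report too.

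**Conclusion.** The point holds as a conditional one. The adjustment rule for the primary test is driven by the outcome and left open, and its effect on the error rate depends on a choice the plan does not make:

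- selection ignoring CF: about 1–6%;
- three named candidates under less favourable readings, such as CF in the selection model: roughly 6–13%;
- about eight candidates with CF in the selection model: about 8–20%.

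These figures rest on an assumed two-sided 5% level, the entry thresholds, a 0–1 SD shift and, for the last line, the assumed pool. They do not show that the analysis as written exceeds 5%. What is certain is that the reported p-value and interval take no account of the selection step. Separately, adding PTH, FGF-23 or binding protein can change which CF effect is estimated. This is a cheap improvement to the plan, not a demonstrated error in it.

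**What to change.** In Section 14.3 and the synopsis:

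1. Limit the primary CF model to the covariates already named: age, gender, one stated body-size measure and baseline 25(OH)D. Justify any change to that set, including dropping baseline 25(OH)D or adding race, before the clearance data are examined.
2. Delete the clause admitting "other covariates strongly related to" clearance from the primary test.
3. State that the primary model targets the CF effect not adjusted for PTH, FGF-23 or binding protein.
4. Report models that add those markers separately and label them exploratory. The planned exploration of clearance can stay as it is.

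Section 14.4 then carries the same fixed set to the secondary endpoints. The cost is a change of wording, with no new data or participants. The downside is possibly slightly less variance explained if an omitted covariate is a strong predictor of clearance.
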